## **7.4.2 Follow-up of Unresolved Adverse Events**

Any AEs that are unresolved at the subject's last AE assessment or other assessment/visit as appropriate in the study are followed up by the investigator for as long as medically indicated, but without further recording in the eCRF. MedImmune retains the right to request additional information for any subject with ongoing AE(s)/SAE(s) at the end of the study, if judged necessary.

## **7.4.3 Recording of Adverse Events of Special Interest**

### **7.4.3.1 Hepatic Function Abnormality**

Events of hepatic function abnormality (as defined in Section 7.6.2) should be recorded in the eCRF according to the definitions of AE and SAE (Section 7.1 and Section 7.2, respectively):

- If the underlying diagnosis for the hepatic function abnormality is known (including progression of pre-existing disease such as primary or metastatic malignancy), the diagnosis should be recorded as an AE/SAE per Section 7.4.

If the underlying diagnosis for the hepatic function abnormality remains unknown, the term "hepatic function abnormal" should be used to report the AE/SAE per Section 7.4.

### **7.4.3.2 Capillary Leak Syndrome**

Events of CLS (as defined in Section 7.3.1) should be recorded in the eCRF according to the definitions of AE and SAE (Section 7.1 and Section 7.2, respectively).

### **7.4.3.3 Thrombotic Microangiopathy/Hemolytic Uremic Syndrome**

Events of thrombotic microangiopathy/HUS (as defined in Section 7.3.2) and HUS-like events should be recorded in the eCRF according to the definitions of AE and SAE (Section 7.1 and Section 7.2, respectively).

### **7.4.3.4 Ocular Events**

Ocular events (as defined in Section 7.3.3) should be recorded in the eCRF according to the definitions of AE and SAE (Section 7.1 and Section 7.2, respectively).

## 7.5 Reporting of Serious Adverse Events

**Within 24 hours of identifying an SAE, regardless of the presumed relationship to the investigational product, the investigator or qualified designee must complete the SAE Report Form and fax it to MedImmune Patient Safety or designee.**

MedImmune contact information:

The sponsor is responsible for reporting certain SAEs as expedited safety reports to applicable regulatory authorities, ethics committees, and participating investigators, in accordance with ICH Guidelines and/or local regulatory requirements. The sponsor may be required to report certain SAEs to regulatory authorities within 7 calendar days of being notified about the event; therefore, it is important that investigators submit additional information requested by the sponsor as soon as it becomes available.

Investigators should provide all available information at the time of SAE Report Form completion. Investigators should not wait to collect additional information to fully document the event before notifying MedImmune Patient Safety of an SAE. When additional information becomes available, investigators should submit a follow-up SAE Report Form (separate from the initial report form) with the new information. Any follow-up information to an SAE also needs to be provided to MedImmune Patient Safety within 24 hours of learning of the new information.

## 7.6 Other Events Requiring Immediate Reporting

### 7.6.1 Overdose

An overdose is defined as a subject receiving a dose of investigational product in excess of that specified in the Investigator's Brochure, unless otherwise specified in this protocol.

Any overdose of a study subject with the investigational product, with or without associated AEs/SAEs, is required to be reported within 24 hours of knowledge of the event to MedImmune Patient Safety or designee using the Safety Fax Notification Form (Section 7.5 for contact information). If the overdose results in an AE, the AE must also be recorded on the AE eCRF (Section 7.4). Overdose does not automatically make an AE serious, but if the

consequences of the overdose are serious, for example death or hospitalization, the event is serious and must be reported as an SAE (Section 7.4 and Section 7.5). MedImmune does not recommend specific treatment for an overdose. The investigator will use clinical judgment to treat any overdose.

### 7.6.2 Hepatic Function Abnormality

AEs of hepatic function abnormality of special interest to the sponsor are defined as any increase in ALT or AST to greater than  $3 \times \text{ULN}$  **and concurrent** increase in bilirubin to greater than  $2 \times \text{ULN}$  (ie, Hy's law cases). Concurrent findings are those that derive from a single blood draw or from separate blood draws taken within 8 days of each other. In the event of hepatic function abnormality where the etiology is unknown, timely follow-up investigations and inquiries should be initiated by the investigational site, based on medical judgment, to make an informed decision regarding the etiology of the event.

If the underlying diagnosis for the hepatic function abnormality is known (including progression of pre-existing disease such as primary or metastatic malignancy), the diagnosis should be recorded as an AE/SAE.

If the underlying diagnosis for the hepatic function abnormality remains unknown, the term "hepatic function abnormal" should be used to report the AE/SAE.

[REDACTED]

The investigator will review the data with the medical monitor. The investigator should then use clinical judgment to establish the cause based on local standard of care and follow the subject by conducting testing as clinically indicated.

- If, after appropriate workup, in the opinion of the investigator, the underlying diagnosis for the abnormality remains unexplained, or is considered attributable to investigational product, permanent discontinuation of dosing for the study subject should be considered.

Each reported event of hepatic function abnormality will be followed by the investigator and evaluated by the sponsor.

### 7.6.3 Pregnancy

Pregnancy in a female subject who has received investigational product is required to be reported **within 24 hours of knowledge of the event** to MedImmune Patient Safety or designee using the Safety Fax Notification Form (see Section 7.5 for contact information).

Subjects who become pregnant during the study period must not receive additional doses of investigational product and will be withdrawn from the study. The pregnancy will be followed for outcome of the mother and child (including any premature terminations) and should be reported to MedImmune Patient Safety or designee after outcome.

Should the investigator become aware of a pregnancy in the partner of a male study subject who has received investigational product this should be reported **within 24 hours of knowledge of the event** to MedImmune Patient Safety or designee using the Safety Fax Notification Form (see Section 7.5 for contact information). The sponsor will endeavor to collect follow-up information on such pregnancies provided the partner of the study subject provides consent.

### 7.6.4 Other Adverse Events of Special Interest

If any AESIs defined in Section 7.3 require immediate reporting to Patient Safety, including the following: Events of CLS, HUS and ocular events (as defined in Section 7.3) are required to be reported **within 24 hours of knowledge of the event** to MedImmune Patient Safety using the SAE Report Form, even if the event is considered to be non-serious (see Section 7.5 for contact information).

## 7.7 Safety Management During the Study

The MedImmune medical monitor has primary responsibility for the ongoing medical review of safety data throughout the study. This includes review of SAEs and timely review of AEs and “other events” reported during the study. MedImmune Patient Safety is responsible for the receipt, immediate review, investigation, and follow-up of SAEs and other immediately reportable events (eg, overdose and pregnancies) reported from the clinical study sites.

A DMC will be convened to review the study data after the first 15 subjects have been treated at a dose level of 40 µg/kg. The DMC will continue to evaluate safety at a frequency of at least every 6 months during the study to identify any safety signals (Section 13.7).

## 8 PHARMACEUTICAL INFORMATION

**Other Names:** CAT-8015, HA22

**Classification:** Recombinant anti-CD22 MAb Conjugated Immunotoxin

**Molecular Weight:** 63.5 kDa

**Mode of Action:** Moxetumomab pasudotox specifically binds to CD22 on the cell surface of B cells. Following binding, the complex is endocytosed and then processed to release the exotoxin. The exotoxin domain is translocated to the cytosol, where it catalyzes the adenosine diphosphate ribosylation of elongation factor 2, causing inhibition of protein translation and subsequent cell death.

**Description:** Moxetumomab pasudotox is a recombinant conjugated immunotoxin composed of a disulfide-stabilized anti-CD22 Ig Fv genetically fused to a truncated form of *Pseudomonas* exotoxin, PE38.

[REDACTED]

[REDACTED]

[REDACTED]

[REDACTED]

[REDACTED]

[REDACTED]

[REDACTED]

[REDACTED]

[REDACTED]

**Route of Administration:** IV infusion

[REDACTED]

[REDACTED]

[REDACTED]

**8.1 Additional Study Medications**

No other study medications are specified for use in this clinical protocol.

**8.2 Labeling**

Labels for the investigational product will be prepared in accordance with Good Manufacturing Practice (GMP) and local regulatory guidelines. Label text will be translated into local languages, as required.

**8.3 Treatment Compliance**

Investigational product is administered by study site personnel, who will monitor compliance.

## 8.4 Accountability

The investigator's or site's designated investigational product manager is required to maintain accurate investigational product accountability records. Upon completion of the study, copies of investigational product accountability records will be returned to MedImmune. All unused investigational product will be returned to a MedImmune-authorized depot or disposed of upon authorization by MedImmune.

## 9 BIOMARKER, CORRELATIVE, AND SPECIAL STUDIES

### 9.1 Pharmacokinetic Studies

#### 9.1.1 Moxetumomab Pasudotox PKs

A laboratory manual will be provided to the sites that specifies the procedures for collection, processing, storage, and shipment of samples, as well as laboratory contact information, specific to this clinical research study.

[REDACTED]

[REDACTED]

[REDACTED]

[REDACTED]

[REDACTED]

[REDACTED]

## 9.2 Laboratory Correlative Studies

A laboratory manual will be provided to the sites that specifies the procedures for collection, processing, storage, and shipment of samples, as well as laboratory contact information, specific to this clinical research study.

### 9.2.1 Evaluation of Immunogenicity

[REDACTED]

[REDACTED]

### 9.2.2 Bone Marrow Aspirate Minimal Residual Disease Analysis

[REDACTED]

[REDACTED]

[REDACTED]

### 9.2.3 Peripheral Blood Flow Cytometry

[REDACTED]

### 9.2.4 Lymphocyte Enumeration

[REDACTED]

### 9.2.5 Peripheral Blood Disease B-cell Clone Detection

[REDACTED]

## 9.3 Sample Storage, Tracking, and Disposition

All research samples will be used for the assays specified in this protocol. The assays will be performed using the entire sample designated for the particular study.

The PI would be notified upon discovery of sample loss or unplanned destruction associated with unforeseen problems such as, but not limited to, natural disasters, laboratory or equipment malfunctions and human error. The PI (or designee) would in turn notify the IRB.

All patient samples that are shipped to [REDACTED] and stored must have patient identifying information removed to maintain patient anonymity. These samples will be used only for purposes described in the protocol and informed consent form and remaining samples will be destroyed at the end of the study. Assay results will be kept in a secure database prior to disclosure in the final study report and any public disclosure (manuscripts, presentations, etc).

**Table 10-1 Study Calendar for Cycle 1 and Subsequent Cycles**

Evaluation/Intervention	Screening a	Pre-cycle b	Day 1	Day 3	Day 5	Day 8 (±1D)	Day 15 (±2D) c	Day 21 (±2D) c
█	█	█	█	█	█	█	█	█
█	█	█	█	█	█	█	█	█
█	█	█	█	█	█	█	█	█

**Table 10-2 Study Calendar for End of Treatment and Follow-up**

Evaluation/Intervention	EOT a	From end of treatment assessment					Yearly Thereafter (± 1M)
		Every month for 6 months (if in CR) (± 1W)	Every 3 months for 24 months (± 2W)	181D (+ 2W)	12 months (± 1M)	18 months (± 1M)	
History and Physical exam	X			X	X	X	X
Vital signs including pulse oximetry and weight	X			X	X	X	X
Performance Status	X			X	X	X	X
Concurrent medications	X			X	X b	X b	X b
Adverse events	X						
Ophthalmologic exam	X						
12-lead ECG (analyzed by central vendor ERT)	X						
Imaging with CT or MRI of abdomen c	X			X		X	
BM biopsy and aspirate (flow cytometry/sequencing)	X			X d			
Clinical response assessment			X		X	X	X
CBC with differential (no peripheral blood smear)	X	X e	X e	X	X	X	X
Chem 7 (sodium, potassium, chloride, bicarbonate, glucose, BUN, creatinine)	X			X	X	X	X
Mineral panel (calcium, magnesium, phosphorous, albumin)	X			X	X	X	X
Hepatic panel (AST, ALT, total bilirubin, direct bilirubin, AlkPhos)	X			X	X	X	X
Uric acid, LDH, total protein, triglycerides, cholesterol, GGT, PT, PTT, fibrinogen, quantitative immunoglobulins, CK, CRP, serum ferritin	X			X			
TSH, fT4, serum amylase, serum lipase, haptoglobin, urinalysis	X			X			
████████████████████	█						

**Table 10-2 Study Calendar for End of Treatment and Follow-up**

Evaluation/Intervention	EOT a	From end of treatment assessment					Yearly Thereafter (± 1M)
		Every month for 6 months (if in CR) (± 1W)	Every 3 months for 24 months (± 2W)	181D (+ 2W)	12 months (± 1M)	18 months (± 1M)	
[REDACTED]	■			■	■	■	■
[REDACTED]	■			■			

AlkPhos = alkaline phosphatase; ALT = alanine transaminase; AST = aspartate aminotransferase; BM = bone marrow; BUN = blood urea nitrogen; CBC= complete blood count; CK = creatinine kinase; CR = complete response; CRP = C reactive protein; CT = computed tomography; D = day; ECG = electrocardiogram; EOT = end of treatment; GGT = gamma-glutamyl transferase; LDH = lactate dehydrogenase; M = month; MRI = magnetic resonance imaging; PT = prothrombin time; PTT = partial thromboplastin time; TSH = thyroid stimulating hormone; W = week.

- a End of treatment is 28-42 days after the first dose of the last cycle. At the discretion of the investigator, a full disease assessment may be performed prior to completion of 6 cycles of therapy if the patient maintains blood counts needed for CR for at least 4 weeks. This interim assessment will include all assessments required at EOT.
- b Only to collect blood component transfusions and hematopoietic growth factors uses.
- c CT or MRI abdomen at 6 and 18 month time points after EOT. Subjects enrolled in Germany will utilize MRI for all radiographic assessments (CT not permissible).
- d This assessment is required 6 months after EOT only for patients in CR or PR.
- e Patients in CR will have a CBC with differential (no peripheral blood smear) monthly from the EOT assessment until the 181D assessment, then every 3 months for 24 months, then every 6 months thereafter. For patients not in CR, repeat CBC with differential (no peripheral blood smear) every 3 months for 24 months after the end of treatment, and every 6 months thereafter.

[REDACTED]

## 11 MEASUREMENT OF EFFECT

For the purposes of this study, patients will receive up to 6 cycles of therapy as described in Section 5.3. Bone marrow examination and radiographic disease assessment will be performed at screening, the end of treatment, and 6 months post-end of treatment. If during treatment and prior to completion of 6 cycles of therapy, blood counts are consistent with CR for at least 4 weeks, an interim disease assessment may be performed at the discretion of the investigator. If a CR without MRD is documented, treatment will be discontinued. For any other response, treatment should be continued to complete 6 cycles of therapy, with the full disease assessment repeated at EOT (Table 10-2).

### 11.1 Response Criteria

Following the end of treatment, 6 month post-end of treatment, and interim (during treatment; if applicable) disease assessment, the Principal or Associate Investigator will record the tumor response. Responses include: CR with or without MRD, PR, stable disease (SD), PD, and relapse. The Principal or Associate Investigator will also record the clinical response prior to each treatment cycle, and at each follow-up visit after the 6 month post-end of treatment assessment. PD may only be used during therapy. Once a subject has ended therapy, worsening of disease no longer meeting criteria for best response will be designated as disease relapse. Response criteria will be based on previous HCL studies ([Cheson et al, 1998](#); [Grever et al, 1995](#); [Hoffman et al, 1997](#); [Catovsky et al, 1987](#)). Although the requirements varied slightly among these trials, certain requirements are well accepted and considered standard. Isolated laboratory values not consistent with a response may be ignored in the assessment of a response, at the discretion of the investigator, if preceded and followed by the values for the same laboratory that are consistent with the identified response, or if they occur within the first 12 days of the cycle. The CBC used as a baseline for determining improvement is generally the last one prior to drug, unless that CBC is not representative of others immediately preceding it and is thought to contain lab errors. Response is verified independently through a central disease response assessment vendor to be determined.

#### Complete Response with or without Minimal Residual Disease

CR  $\pm$  MRD requires all of the following to be present:

- No evidence of leukemic cells in the peripheral blood and/or by routine H/E staining of bone marrow. Minimal Residual Disease: CR with HCL evident in blood or marrow by flow cytometry or in bone marrow biopsy by immunohistochemistry (**NOTE:** A second confirmatory bone marrow examination is not required).

- Resolution of any hepatomegaly, splenomegaly, and abnormal ( $\geq 2$  cm minimum length) lymphadenopathy by CT or MRI. Although a normal spleen size is not defined, the maximum diameter of the spleen should be either  $< 17$  cm or have decreased by  $>25\%$  from its baseline.
- Normal CBC as exhibited by: Neutrophils  $\geq 1.5 \times 10^9/L$ , Platelets  $\geq 100 \times 10^9/L$ , and Hemoglobin  $\geq 11.0$  g/dL without transfusions or growth factors for at least 4 weeks.

### **Definition of Hematologic Remission**

HR is defined as the blood counts required for CR. The primary endpoint requires that CRs maintain HR for  $>180$  days after first achieving CR. Once a CR is achieved, the HR duration is not interrupted by transient decreases in normal blood counts.

### **Complete Response Duration**

The duration of complete remission is calculated from the time of achievement of all criteria of CR to the time of relapse from CR. Relapse from CR will be defined as any CR criteria (blood counts, imaging or bone marrow) no longer consistent with CR. However, to meet the primary endpoint, patients will need to achieve CR and then maintain a HR for  $>180$  days.

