### **Relapse**

- Relapse from CR: Loss of criteria needed for CR, excluding transient decrease in lab values below criteria for CR.
- Relapse from PR: Loss of criteria needed for PR, excluding transient decrease in lab values below criteria for PR.
- Relapse from SD: Patients who meet above criteria for PD when compared to measurements after end of therapy.

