#### **13.4.1.1 CR Rate, Duration of CR (Disease-Free Survival), and Duration of Hematologic Remission**

The CR rate is defined as the proportion of subjects that have achieved CR. The 95% CI of the CR rate will be constructed using the exact probability method (Clopper-Pearson exact interval). Duration of CR (also called disease-free survival) will be measured from the first documentation of CR (by imaging, bone marrow biopsy and blood counts) to the time of relapse as defined in Section 11.1. Duration of HR will be measured from the first documentation of CR (by imaging, bone marrow biopsy and blood counts) to the time of loss of HR. Duration of CR will be censored on the date of the last disease assessment or clinical

response assessment for subjects who have no documented relapse prior to data cutoff, dropout, or the initiation of alternative anticancer therapy. Duration of HR will be censored on the date of the last evaluable hematologic assessment for subjects who have no documented loss of HR prior to data cutoff, dropout, or the initiation of alternative anticancer therapy. The proportion of subjects with a CR and HR at certain time points (eg, 6 month, 1 year, or 2 year) and the median duration of CR and HR may be estimated, if feasible, for the subgroup of subjects with CR using the Kaplan-Meier method. It should be noted that CR duration, which may be shorter than HR duration, is a secondary endpoint and will be summarized separately.

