#### **13.4.1.4 Duration of Objective Response**

Duration of objective response will be measured from the first documentation of objective response to the event of relapse as defined in Section 11.1. Duration of objective response will be censored on the date of last disease assessment for subjects who have no documented relapse prior to data cutoff, dropout, or the initiation of alternative anticancer therapy. Duration of objective response will be summarized descriptively by using minimum and maximum of duration of objective response observed at a certain follow-up period. The proportion of subjects with response at certain time points (eg, 6 month, 1 year, or 2 year) and the median duration of response may be estimated, if feasible, for the subgroup of subjects with objective response using the Kaplan-Meier method.

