#### **13.4.1.5 Progression-Free Survival**

PFS is measured from the start of moxetumomab pasudotox administration to relapse, PD, or death from any cause. Relapse is considered post-end of treatment when patients no longer meet criteria required for their best response (Section 11.1). PFS will be censored on the last hematologic assessment for subjects without relapse, PD, or death. PFS will be evaluated using the Kaplan-Meier method.

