#### **13.4.1.6 Time to Treatment Failure**

TTF will be measured from the start of moxetumomab pasudotox administration until relapse, PD, initiation of alternate cancer therapy, or death due to disease or disease-related complication. ([Else et al, 2009](#)). TTF will be censored as in PFS but will also be censored for death not accompanied by relapse, and will also be evaluated using the Kaplan-Meier method.

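### Section 11.1 defines relapse from CR in two inconsistent ways, with and without an exclusion for transient laboratory decreases, and the secondary duration and time-to-event endpoints do not say which applies

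*Protocol*

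**What the plan says.** The two definitions stand a few paragraphs apart in Protocol Section 11.1:

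- Complete Response Duration: "Relapse from CR will be defined as any CR criteria (blood counts, imaging or bone marrow) no longer consistent with CR".
- Relapse: "Relapse from CR: Loss of criteria needed for CR, excluding transient decrease in lab values below criteria for CR".

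Two other statements in Section 11.1 bear on low counts. The introduction carries a general allowance: "Isolated laboratory values not consistent with a response may be ignored in the assessment of a response, at the discretion of the investigator". It covers values with consistent results before and after, and values early in a cycle. The definition of hematologic remission says: "Once a CR is achieved, the HR duration is not interrupted by transient decreases in normal blood counts".

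The endpoint sections rely on relapse as follows:

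- Duration of CR (13.4.1.1) runs "to the time of relapse as defined in Section 11.1".
- Duration of objective response (13.4.1.4) runs "to the event of relapse as defined in Section 11.1".
- PFS (13.4.1.5) counts relapse after the end of treatment when the best-response criteria are no longer met. It also cites Section 11.1, and its own sentence has no transient exception.
- TTF (13.4.1.6) runs "until relapse, PD, initiation of alternate cancer therapy, or death due to disease or disease-related complication", with no reference for relapse.

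**The concern.** The CR criteria include neutrophil, platelet and hemoglobin thresholds. Patients in CR have a CBC every month to Day 181 and every 3 months after that (Sections 3.3.4.2 and Table 10-2), so a passing value below a threshold has many chances to occur. Read literally, the Complete Response Duration sentence ends CR at that value. The Relapse paragraph does not. A reference to Section 11.1 as a whole cannot settle the matter, because both rules are in it.

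At stake is the event date, and sometimes the event itself, in four secondary endpoints. The literal reading would shorten CR duration and add events to PFS, to TTF and to duration of objective response among CR patients, with no lasting loss of remission behind them. Two analysts could each follow the protocol and report different Kaplan-Meier curves.

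**Working it through.** **Plan's own figure.** Sections 13.3 and 13.5 state 90% power with 77 subjects for 28% against 13% at two-sided 0.05. In an exact single-arm binomial test, the smallest number of durable CRs with upper-tail error at most 0.025 under 13% is 17 of 77 (upper-tail error 0.0189). Power at 28% is 0.903. The figure reproduces, and the present point does not touch it.

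**Side-by-side reading.** Take a patient in CR whose hemoglobin is just under the 11.0 g/dL threshold at one monthly CBC and above it at the CBCs before and after, with imaging and marrow unchanged.

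| Text in Section 11.1 | Result |
|---|---|
| Complete Response Duration | A CR criterion is not met: relapse on that date |
| Relapse | Transient laboratory decrease: no relapse |
| Introduction | The investigator may ignore the value, but need not |
| Definition of hematologic remission | HR continues |

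The first two rows disagree, and both claim to define relapse from CR. Both are current text, and redaction does not explain the difference.

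**Which endpoints are reached.**

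- Duration of CR: directly.
- Duration of objective response: only for patients whose response is CR, because relapse from PR is defined once.
- PFS and TTF: through their relapse component, for patients in CR.
- Durable CR (primary): not reached. It needs CR followed by HR for more than 180 days, and HR has its own tolerance.

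**Illustration of size.** The documents give no rate of transient dips. Assume a probability q per CBC, independent between CBCs, that a patient still in remission shows a transient sub-threshold value. The chance of at least one dip over m CBCs is 1 − (1 − q)^m. For m, monthly CBCs to Day 181 give about 6. The 3-monthly phase adds 6 if the two years run from the end of treatment (m = 12), or 8 if they start at Day 181 (m = 14).

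| q | m = 6 | m = 12 | m = 14 |
|---|---|---|---|
| 2% | 1 − 0.98^6 = 11.4% | 1 − 0.98^12 = 21.5% | 24.6% |
| 5% | 1 − 0.95^6 = 26.5% | 1 − 0.95^12 = 46.0% | 51.2% |
| 10% | 1 − 0.90^6 = 46.9% | 1 − 0.90^12 = 71.8% | 77.1% |

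These are the shares of CR patients who would have a relapse date under the first definition on a transient value alone. Under the second definition as worded the share is zero. Positive correlation of dips within a patient lowers the figures.

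**The case against.** The best defence is that the two texts can be read together. The Complete Response Duration sentence can be taken as a list of the domains that end CR (counts, imaging, marrow), set against HR, which depends on counts alone. On that view it is silent on transient values, and the paragraph headed Relapse is the natural target of the references in Section 13.4.1. The rest of the protocol leans the same way. The Précis asks for a repeat marrow to confirm relapse when cytopenias are sustained, and HR tolerates transient dips. This is good evidence of what was intended. It does not remove the conflict, because the outlying sentence sits in the very paragraph that defines CR duration and says that any criterion suffices.

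A reader might also infer more than the documents support:

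- *That the primary result is at risk.* It is not, because HR has its own rule.
- *That Section 11.1 holds three definitions of relapse.* The introductory sentence is a discretionary laboratory allowance for assessing response, not a definition of relapse. It softens the first definition without resolving the conflict: it is optional and left to the investigator, while central review is the basis of the primary analyses (Section 13.3).
- *That every dip would be called relapse and the patient taken off study.* Section 5.5 asks for confirmation of relapse. Section 5.4 describes clinical relapse in CR patients through loss of HR, symptoms or organomegaly. An unconfirmed single dip does not clearly meet this under either wording.
- *That the percentages are forecasts.* Both the rates and the independence are assumed.

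Leaving the matter to the SAP is not a full answer. The protocol has not left a detail open; it states two rules that give different results.

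**Conclusion.** The point stands as an inconsistency that is wrong as written and should be corrected. It is confined to secondary endpoints: duration of CR, duration of objective response in CR patients, PFS and TTF. The textual conflict rests on no assumption. Its numerical effect cannot be derived from the protocol. Under the assumed 2% to 10% independent dip rates, roughly one in nine to nearly one half of CR patients would be classified differently over 6 CBCs, and about one fifth to seven tenths over 12. Clustering would reduce both ranges. The primary analysis and its stated power are unaffected.

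**What to change.** In Section 11.1, replace the relapse sentence under Complete Response Duration with a reference to the Relapse paragraph, so that transient laboratory decreases are excluded. Cite that single definition in Sections 13.4.1.1, 13.4.1.4, 13.4.1.5 and 13.4.1.6; TTF needs it as much as the others. State that the central review gives *transient* the same meaning for relapse from CR as for HR, so that one CBC cannot be tolerated for HR and yet end CR.

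A new rule for CR relapse alone, such as ignoring a value only when both neighbouring CBCs meet CR, is not needed to remove the conflict. It could separate CR relapse from HR again, because two consecutive low values might be tolerated for one and not for the other. Any such operational limit should cover both.

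The cost is one replaced sentence in Section 11.1, four cross-references and one sentence on central review. No new data or visits are required.
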